### **Additional suggestions for sensitivity analyses**

Other suggestions for additional sensitivity analyses may include analyses to check for potential bias in follow-up schedules for tumor assessments, e.g. by assigning the dates for censoring and events only at scheduled visit dates. The latter could be handled by replacing in Table 14-5 the “Date of last adequate assessment” by the “Date of previous scheduled assessment (from baseline)”, with the following definition:

- **Date of previous scheduled assessment (from baseline)** is the date when a tumor assessment would have taken place, if the protocol assessment scheme was strictly followed from baseline, immediately before or on the date of the last adequate tumor assessment.

In addition, analyses could be repeated using the Investigators’ assessments of response rather than the calculated response. The need for these types of sensitivity analyses will depend on the individual requirements for the specific study and disease area and have to be specified in the protocol or RAP documentation.

#### **14.2.19 Data handling and programming rules**

The following section should be used as guidance for development of the protocol, data handling procedures or programming requirements (e.g. on incomplete dates).

#### **14.2.20 Study/project specific decisions**

For each study (or project) various issues need to be addressed and specified in the protocol or RAP documentation. Any deviations from protocol must be discussed and defined at the latest in the RAP documentation.

The proposed primary analysis and potential sensitivity analyses should be discussed and agreed with the health authorities and documented in the protocol (or at the latest in the RAP documentation before database lock).

#### **14.2.21 Treatment and study completion CRFs**

If study drug is discontinued, the **treatment completion page** is to be completed with a visit date reflecting the date the discontinuation decision was made, and with the 'Last known date subject took study drug' and one of the following reasons:

- Adverse event(s)
- Abnormal laboratory value(s)
- Abnormal test procedure results(s)
- Protocol violation
- Subject withdrew consent
- Lost to follow-up
- Administrative problems
- Death
- Disease progression
- Treatment duration completed as per protocol (optional, to be used if only a fixed number of cycles is given)

For reasons other than progression (and death) it should be checked if this was not in fact progression (especially reasons Adverse Events, Abnormal laboratory value (s), Abnormal test procedure result and subject withdrew consent). Also it should be checked if patient withdrew consent because of safety issues, in which case reasons Adverse Events, Abnormal laboratory value (s), Abnormal test procedure result should be used.

All patients who discontinued study drug for reasons other than documented progression, death or lost to follow-up will be followed for progression thereafter (patients who withdrew consent might not be followed with regular tumor assessments at the study site, but should ideally be followed until progression outside the study site). Ideally, all patients who discontinued study drug for progression without documented progression will still be followed with regular tumor assessments (e.g. in case of central radiology review). During that evaluation period, usually only tumor measurements (and/or response status) and survival data are collected. In some protocols, the subsequent anti-cancer therapies may also be recorded.

At the end of the study evaluation period, the **study evaluation completion page** is filled out with the following options:

- Subject withdrew consent
- Lost to follow-up

- Administrative problems (when follow-up for progression has met protocol required events, e.g. follow-up stopped at certain number of events or certain time)
- Death
- New cancer therapy (optional, to be used when follow-up for progression is stopped in this case)
- Disease progression

Thereafter, patients will be followed for survival using the survival follow-up pages. If information on death becomes available for patients who were lost to follow-up or withdrew consent, this may also be entered in the database. The reason for death must be documented (and will be coded using MedDRA); it must be also stated if death was due to 'Study indication' or 'Other' reason.

In comparative studies with long follow-up period and therefore extended visit schedule, it may be useful to collect the survival status at a pre-specified cut-off within a limited timeframe for all patients with no documented death. In this case, this requires a contact to be made with the patient or with any reliable source of information on the patient's status, but not requiring a specific visit to be scheduled

Until the specified cut-off point has been reached, the goal is to collect tumor assessments until disease progression for all patients regardless of whether the patients are still receiving study drug. If patients are not followed for progression, e.g. in a Phase I or II study mainly evaluating safety, the evaluation is completed when study drug is completed (in this case only the first completion page is used).

#### **14.2.22 Medical validation of programmed overall lesion response**

As RECIST is very strict regarding measurement methods (i.e. any assessment with more or less sensitive method than the one used to assess the lesion at baseline is considered UNK) and not available evaluations (i.e. if any target or non-target lesion was not evaluated the whole overall lesion response is UNK unless remaining lesions qualified for PD), these UNK assessments may be re-evaluated by clinicians at Novartis or external experts. In addition, data review reports will be available to identify assessments for which the investigators' opinion does not match the programmed calculated response based on RECIST criteria. This may be queried for clarification. However, the investigator response assessment will never be overruled.

If Novartis elect to invalidate an evaluation of overall lesion response upon internal or external review of the data, the calculated overall lesion response at that specific assessment is to be kept in a dataset. This must be clearly documented in the RAP documentation and agreed before database lock. This dataset should be created and stored as part of the 'raw' data.

Any discontinuation due to 'Disease progression' without documentation of progression by RECIST criteria should be carefully reviewed. Only patients with documented deterioration of symptoms indicative of progression of disease should have this reason for discontinuation of treatment or study evaluation.

### **14.2.23 Programming rules**

The following should be used for programming of efficacy results:

### **14.2.24 Calculation of 'time to event' variables**

Time to event = enddate - startdate + 1 (in days)

When no post-baseline tumor assessments are available, the date of randomization/start of treatment will be used as enddate (duration = 1 day) when time is to be censored at last tumor assessment, i.e. time to event variables can never be negative.

### **14.2.25 Incomplete assessment dates**

All investigation dates (e.g. X-ray, CT scan) must be completed with day, month and year.

If one or more investigation dates are incomplete but other investigation dates are available, this/these incomplete date(s) are not considered for calculation of the assessment date (and assessment date is calculated as outlined in [Section 14.2.17](#)). If all measurement dates have no day recorded, the 1st of the month is used.

If the month is not completed, for any of the investigations, the respective assessment will be considered to be at the date which is exactly between previous and following assessment. If a previous and following assessment is not available, this assessment will not be used for any calculation.

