## 7.2 Assessment types

### 7.2.1 Efficacy assessments

#### Core Phase

Patients should have either at least one lesion that can be measured as per RECIST 1.0 criteria OR have bone lesions: lytic or mixed (lytic + sclerotic) in the absence of measurable disease as defined above.

For patients with measurable disease at baseline (as per RECIST 1.0 criteria), efficacy (overall tumor response and progression) will be evaluated every 8 weeks (+/- 1 week) during the Core Phase according to the RECIST 1.0 criteria. If an initial observation of response is made, a confirmation scan (or photography for measurable skin lesions) should be obtained at least 4 weeks after the initial observation. All patients being discontinued from the study for disease progression must have their progression documented using the criteria specified in [Appendix 2](#). All patients who discontinue study treatment for any reason (i.e., an adverse event, administrative reasons etc) other than disease progression or consent withdrawal will continue to have tumor assessments per the schedule during the Core Phase until disease progression or until new anti-cancer therapy is initiated.

All primary and secondary endpoints based on radiological (and photographic when applicable) assessments of tumor burden will be derived using the local (treating centers) radiologist's / investigator's assessment.

A bone scan or a skeletal survey should be performed at baseline for all patients within 28 days of enrollment. Any abnormalities (i.e., hotspots) identified on the bone scan must be confirmed by X-ray, CT scan with bone windows or MRI. Bone lesions identified at baseline should follow the same assessment schedule as for measurable lesions. Additional bone scans or skeletal surveys should be performed if clinically indicated. Abnormalities found on subsequent bone scans must also be confirmed by X-ray, CT scan or MRI.

The same method of assessment and the same technique should be used to characterize each identified and reported lesion at baseline for each study tumor assessment after start of study treatment.

If possible, each center should have a designated radiologist responsible for the interpretation of CT or MRI scans and the evaluation according to RECIST 1.0 criteria (see [Appendix 2](#) for details). The same radiologist/physician should perform the evaluation for the entire duration of the study. All radiology evaluations will be performed initially by the local radiologist.

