### **10.4.1 Variable**

The primary efficacy endpoint in this study is PFS, defined as the time from the date of enrollment to the date of first documented progression or death due to any cause. If a patient has not had an event, PFS will be censored at the date of the last adequate tumor assessment. See RECIST, [Appendix 2](#). The primary efficacy endpoint will be assessed as per local radiological assessment.

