**Table 14-5 Options for event dates used in PFS, TTP, duration of response**

Situation		Options for end-date (progression)  (1) = default unless specified differently in the protocol or analysis plan	Outcome
A	No baseline assessment	(1) Date of randomization/start of treatment	Censored
B	Progression at or before next scheduled assessment	(1) Date of progression (2) Date of next scheduled assessment 	Progressed Progressed
C1	Progression or death after exactly one missing assessment	(1) Date of progression (or death) (2) Date of next scheduled assessment 	Progressed Progressed
C2	Progression or death after two or more missing assessments	(1) Date of last adequate assessment  (2) Date of next scheduled assessment  (3) Date of progression (or death)	Censored Progressed Progressed
D	No progression	(1) Date of last adequate assessment	Censored
E	Treatment discontinuation due to 'Disease progression' without documented progression, i.e. clinical progression based on investigator claim	(1) N/A (2) Date of discontinuation (visit date at which clinical progression was determined)	Ignored Progressed
F	New anticancer therapy given	(1) Date of last adequate assessment (2) Date of secondary anti-cancer therapy	Censored Censored
G	Deaths due to reason other than deterioration of 'Study indication'	(1) Date of last adequate assessment	Censored (only TTP)

 = Definitions can be found in [Section 14.2.17](#).

 = After the last adequate tumor assessment. "Date of next scheduled assessment" is defined in [Section 14.2.17](#).

The primary analysis and the sensitivity analyses must be specified in the protocol. Clearly define if and why options (1) are not used for situations C, E and (if applicable) F.

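### Minor: the missing-month rule in Section 14.2.25 can turn a documented progression into a censored observation, because a progression scan normally has no following assessment

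*Protocol*

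**What the plan says.** Section 14.2.25 works in steps.

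- Complete dates are required: "All investigation dates (e.g. X-ray, CT scan) must be completed with day, month and year".
- If some dates at an assessment are incomplete and others are not, "this/these incomplete date(s) are not considered for calculation of the assessment date".
- If every date lacks only the day, the first of the month is used.
- If the month is missing, "the respective assessment will be considered to be at the date which is exactly between previous and following assessment".
- Without both neighbours there is no imputation: "If a previous and following assessment is not available, this assessment will not be used for any calculation".

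Other parts of the protocol decide what follows from this.

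- Section 7.2.1: patients who stop treatment for reasons other than progression or withdrawn consent "will continue to have tumor assessments per the schedule during the Core Phase until disease progression" or new anti-cancer therapy.
- Section 7.1.3: patients who enter second line start it within 28 days of documented progression and are scanned on the same schedule as before.
- Section 10.4.1: PFS runs from "the date of enrollment to the date of first documented progression or death due to any cause". Without an event it is censored at the last adequate tumor assessment.
- Section 14.2.17: the progression date is the first assessment date with an overall response of progressive disease.
- Table 14-5, situation A ("No baseline assessment"): censoring at the start date.
- Section 14.2.26: a death date with no day is set to the 15th of the month, and the death is kept.

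**The concern.** A missing month makes the date uncertain. It does not make the progression uncertain. The discard clause treats the two alike, and it falls on the ends of the assessment sequence: a mid-course stable-disease scan with the same defect is kept at a midpoint, while a final progression scan is removed.

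For the progression scan the error has one direction. A known event becomes censoring one scan earlier, so PFS comes out too long. PFS by local assessment is the only primary endpoint, and the trial has a single arm, so no control arm offsets an upward error. The same rule would apply to second-line PFS.

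**Working it through.** **1. The plan's own figures.** Section 10.8 gives 200 patients, 18 months of recruitment, 12 months of follow-up and 10% loss. Assume exponential PFS with hazard λ = ln 2 / median, and exponential loss reaching 10% by month 30, so g = −ln(0.9)/30. With t = λ + g:

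- d = 200 × (λ/t) × {1 − [exp(−12t) − exp(−30t)] / (18t)}
- 95% CI = median × exp(±1.96/√d)

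| Median (months) | Expected events d | CI computed | CI in Section 10.8 | Width |
|---|---|---|---|---|
| 11 | 139.7 | 9.32–12.98 | 9.32–12.98 | 3.66 |
| 12 | 133.8 | 10.13–14.22 | 10.13–14.22 | 4.09 |
| 13 | 128.2 | 10.93–15.46 | 10.93–15.46 | 4.53 |
| 14 | 123.1 | 11.73–16.71 | 11.73–16.71 | 4.98 |

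The design table reproduces, so the same model can be used to size the rule.

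**2. Which assessments lack a neighbour.**

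| Assessment with no month on any investigation | Previous? | Following? | Result |
|---|---|---|---|
| Baseline | No | Yes | Not used |
| Mid-course scan | Yes | Yes | Kept at midpoint |
| Progression scan, no later scan | Yes | No | Not used; event lost unless a later death counts |
| First-line progression scan, patient enters second line | Yes | Only if second-line scans count | Midpoint, or not used |

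**3. Size for lost progressions.** Let a share q of progression scans be discarded, each patient being censored one interval earlier. The interval is 8 weeks = 56/30.4375 = 1.84 months. Events fall by the factor (1 − q) and total follow-up by (1 − 1.84qλ), so the estimated median becomes

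median × (1 − 1.84qλ) / (1 − q).

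At q = 1%:

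- 11 months: 11 × 0.99884/0.99 = 11.10, a shift of +0.10
- 12 months: 12 × 0.99894/0.99 = 12.11, a shift of +0.11
- 14 months: 14 × 0.99909/0.99 = 14.13, a shift of +0.13

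About 1.2 to 1.4 events are lost per 1%. Simulating 3,000 trials of 200 patients per setting, with scans every 8 weeks ± 1 week and affected progressions censored at the previous scan, gives these mean shifts in the Kaplan-Meier median (months):

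| True median | 1% | 3% | 5% |
|---|---|---|---|
| 11 | +0.09 | +0.28 | +0.50 |
| 12 | +0.11 | +0.31 | +0.54 |
| 14 | +0.12 | +0.38 | +0.65 |

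At 0.1% the shift is about 0.01 month. The 1% shifts are 0.09/3.66 = 2.5%, 0.11/4.09 = 2.7% and 0.12/4.98 = 2.4% of the planned CI widths.

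A single sample of 400,000 behaves differently. It shows only +0.02 to +0.03 month at 1%, but a jump of about 1.4 months at 2% for a true median of 11, because events cluster at scan times and the median moves in steps. For a trial of 200, the mean over repeated trials is the relevant figure.

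**4. If second-line scans count as following.** Put the true progression scan at day 0, the previous scan at day −56 and second-line start at day s (0 to 28), with the next scan at day s + 56. The midpoint is (−56 + s + 56)/2 = s/2, so progression is dated 0 to 14 days late. If the visit windows shorten the first interval to 49 days and lengthen the second to 63, the midpoint is (s + 14)/2. That falls on or after second-line start when s ≤ 14.

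**5. Baseline.** Each 1% of baselines affected is 200 × 0.01 = 2 patients. If they are censored on day 1 for a reason unrelated to prognosis, the risk set shrinks but the curve keeps its expected position. Simulated shifts at 1% and 5% were below 0.01 month.

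**The case against.** The case for leaving the text alone is strong on frequency. Complete dates are mandatory, Section 9.4 sends queries for missing values, and Section 14.2.25 already says: "If one or more investigation dates are incomplete but other investigation dates are available, this/these incomplete date(s) are not considered". An assessment usually has several dated investigations. For patients going to second line, the progression scan starts a 28-day clock, so the site needs its date. Patients scanned again in second line may have a following assessment, so the simulation, which discards every affected progression, is an upper bound. Section 14.2.19 presents these rules as guidance, and the analysis plan, which is not shown, may replace them. All of this stands and makes the point minor. It does not make the rule right: Section 14.2.23 says the rules should be used for programming efficacy results.

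Three stronger readings are tempting, and the documents do not support them.

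- A reader might infer that the rule deletes baseline and progression scans generally. It acts only when the month is missing and, read with the sentence before it, no other investigation at that assessment is dated.
- A reader might infer that lost baselines also lengthen PFS. PFS starts at enrollment, and day-1 censoring unrelated to prognosis costs precision only. Applying situation A to a baseline that was performed but undated is itself an inference. The case is nearly excluded anyway, since baseline imaging must fall within a 28-day window and the sponsor checks key eligibility before enrollment.
- A reader might infer that the section contradicts itself, because the month sentence can be read as triggered by a single month-less investigation. A coherent reading exists: the earlier sentence covers assessments with another usable date, and the month rule covers the rest. The wording is loose and worth tightening.

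**Conclusion.** The rule is wrong as written, and the defect is minor. In the rare case that a final progression scan has no month on any investigation and queries fail, Section 14.2.25 discards a documented event and biases PFS upward, by about 0.1 month in the median per 1% of progression scans affected. This rests on exponential PFS, the Section 10.8 design assumptions, 8-weekly scans, missingness unrelated to prognosis, and every affected progression being lost. The protocol does not give the rate of missing months. The 1% to 5% range is an assumption used to show scale, and with mandatory dates and queries the true rate is probably well under 1%. At such rates the primary analysis is not undermined. For patients who enter second line, the alternative reading dates progression late rather than losing it. The loss of an undated baseline is a loss of information, not a bias.

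**What to change.** Replace the last paragraph of Section 14.2.25, or override it in the analysis plan, with four statements:

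1. The month rule applies only when no investigation at that assessment has a usable date.
2. A documented progression stays an event. It is dated at the recorded visit date, or otherwise at the scheduled assessment date, bounded after the previous assessment and no later than the end-of-treatment visit, second-line start or death.
3. An undated baseline is kept as the RECIST reference. PFS starts at enrollment and does not need its date.
4. Only a non-progression post-baseline assessment that cannot be bounded is discarded.

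Statement 2 also settles whether a second-line scan may serve as the following assessment for a first-line progression. The cost is one paragraph and a small programming change, with no new data.

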### **14.2.26 Incomplete dates for last contact or death**

All dates must be completed with day, month and year. If the day is missing, the 15th of the month will be used for incomplete death dates or dates of last contact.

### **14.2.27 Non-target lesion response**

If no non-target lesions are identified at baseline (and therefore not followed throughout the study), the non-target lesion response at each assessment will be considered 'not applicable (NA)'.

### **14.2.28 Study/project specific programming**

The standard analysis programs need to be adapted for each study/project.

### **14.2.29 Censoring reason**

In order to summarize the various reasons for censoring, the following categories will be calculated for each time to event variable based on the treatment completion page, the study evaluation completion page and the survival page.

For survival the following censoring reasons are possible:

- Alive (treatment / study evaluation / survival)
- Lost to follow-up (during treatment\* / study evaluation\* / survival)

For PFS and TTP (and therefore duration of responses) the following censoring reasons are possible:

- Ongoing without event (treatment / study evaluation)
- Lost to follow-up (during treatment / study evaluation)
- Withdrew consent (during treatment\* / study evaluation)
- Study evaluation stopped (when follow-up for progression is stopped after certain number of events or at certain time, i.e. reason='Administrative problems' on study evaluation completion page, or when patients are not followed for progression after treatment completion)
- Death due to reason other than underlying cancer (only used for TTP)
- New cancer therapy added (optional; only if the protocol specified that PFS/TTP will be censored at that date)

\*Note = this category is to be used if no further information is available (as information on death may be available in patients who were originally lost to follow-up, and information on progression may be received in patients who withdrew consent to continue study drug).

